3.6. Statistical analysis

Continuous variables will be expressed as mean \pm standard deviation when normally distributed and as median (interquartile range) in case of a non-normal distribution. Normality will be assessed by the Shapiro-Wilk statistic. The independent-samples Student's *t*-test and Mann-Whitney *U* test will be used as indicated to compare between groups. Categorical variables will be expressed as percentages and compared using Fisher's exact test or Pearson's χ^2 -test in case of a non-binary response. Statistical significance will always be set at a 2-tailed probability level of <0.05 . All statistics will be performed using IBM SPSS® (Chicago, Illinois, USA) (version 22.0 for Mac).

4. Potential adverse events

- Metabolic acidosis is the only agent-specific adverse event that might be expected from treatment with acetazolamide. Serum bicarbonate is monitored daily. If serum bicarbonate <22 meq/L, substitution with oral NaHCO_3 will be provided.
- Hyperkalemia might be expected as a potential adverse event of spironolactone, but this medication will be withheld when serum potassium levels are >5.0 mmol/L and serum potassium levels are monitored daily throughout the study.

5. References

- american heart association. *Circulation*. 2013;127:e6-e245
2. Effect of enalapril on survival in patients with reduced left ventricular ejection fractions and congestive heart failure. The solvd investigators. *The New England journal of medicine*. 1991;325:293-302

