3.3. Interventions (See Addendum 1 for therapy schedules)

3.3.1. Arm 1, control group: High-dose loop diuretics

- At the moment of randomization the patient receives an intravenous bolus of loop diuretics at a dose equal to the double of his normal daily oral dose (e.g. a patient who takes 1x1 mg bumetanide will receive 2x1x1 mg = 2mg; or a patient who takes 2x1 mg bumetanide will receive 2x2x1 mg = 4mg).
- The next three days, the patient will receive the same dose equally divided between two administrations at 10u00 and 16u00 provided that the treating physician has concluded during the morning rounds that the patient is still volume overloaded.
- If diuresis since administration of the previous dose of loop diuretics is <1,500 mL and the patient is still volume overload, subsequent bolus doses are doubled.
- If after doubling of the dose, the patient is considered therapy-refractory. The treating physician is recommended to add chlorthalidone 50mg once daily and consider ultrafiltration or renal replacement therapy after which results of the patient will be censored.
- Switch to treatment at the discretion of the treating physician if any of the following criteria is fulfilled
 - After 3 days
 - The patient had no longer clinical signs or symptoms of congestion
 - Doubling of the serum creatinine value

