3.3.2. Arm 1, treatment group: Acetazolamide + low-dose loop diuretics

- At the moment of randomization, the patient receives 500 mg of intravenous acetazolamide and 2 mg of intravenous bumetanide in bolus.
- The next three days, the patient will receive 250 mg of intravenous acetazolamide and 1 mg of intravenous bumetanide in bolus at 10u00 provided that the treating physician has concluded during the morning rounds that the patient is still volume overloaded.

- If diuresis since administration of the previous dose of loop diuretics is <1,500 mL and the patient is still volume overloaded, the patient continues to receive 500 mg of acetazolamide and 2 mg of bumetanide.
- If after doubling of the dose, the patient is considered therapy-refractory. The treating physician is recommended to add chlorthalidone 50mg once daily and consider ultrafiltration or renal replacement therapy after which results of the patient will be censored.
- Switch to treatment at the discretion of the treating physician if any of the following criteria is fulfilled
 - After 3 days
 - The patient had no longer clinical signs or symptoms of congestion
 - Doubling of the serum creatinine value

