3.4. Collected data

- Baseline at the moment of randomization
 - Demographics, medical history, current medical therapy, baseline body weight, blood pressure, heart rhythm (sinus or not), heart rate, Visual-analogue scale (VAS) score for dyspnea and 4-point Likert scale for edema will be assessed upon study inclusion
 - Blood sample: hematocrit, electrolytes, serum osmolality, serum urea, serum creatinine, serum Cystatin C, serum urate, plasma renin activity (PRA), plasma aldosterone, plasma adrenaline, plasma noradrenaline, total protein, plasma NT-proBNP
- Day 1-3:
 - VAS score for dyspnea
 - 4-point Likert scale for edema
 - Body weight and fluid balance
 - Blood pressure, heart rate, heart rhythm
 - Blood sample: hematocrit, electrolytes, serum osmolality, serum urea, serum creatinine, serum Cystatin C, serum urate, PRA, plasma aldosterone, plasma adrenaline, plasma noradrenaline, total protein, plasma NT-proBNP
- Three consecutive 24h urinary collections will be performed; the first one started with the first bolus administration of loop diuretics; urinary assessment of creatinine, protein, sodium, potassium, chloride, ureum, urate, microalbuminuria
- At an outpatient follow-up appointment 2-6 weeks after hospital discharge, a final blood sample with hematocrit, electrolytes, serum osmolality serum urea, serum creatinine, serum Cystatin C, serum urate and plasma NT-proBNP will be collected.
- All-cause mortality and hospital readmissions will be collected prospectively for the study cohort. The patient will receive a telephone call from a study nurse after 3, 6, 9 and 12 months

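### Section 3.6 plans only unadjusted two-sample tests: use the collected baselines in ANCOVA for NT-proBNP, peak hormones and VAS, and name one effect measure with CI for 24 h sodium

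*Combined protocol and SAP*

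**What the plan says.** Section 3.6 is the whole analysis plan. For continuous variables, "Normality will be assessed by the Shapiro-Wilk statistic", and a Student's t or Mann-Whitney U "test will be used as indicated to compare between groups". For the rest, "Categorical variables will be expressed as percentages and compared using Fisher's exact test", or a chi-square test when the response is not binary. The section names no covariate, no regression model, no between-group effect measure and no confidence interval.

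Section 3.4 lists the blood values taken at randomisation, among them "plasma renin activity (PRA), plasma aldosterone, plasma adrenaline, plasma noradrenaline, total protein, plasma NT-proBNP". It also says that "Visual-analogue scale (VAS) score for dyspnea and 4-point Likert scale for edema will be assessed upon study inclusion". The first of the three urine collections has no pre-treatment counterpart: "the first one started with the first bolus administration of loop diuretics".

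Section 3.5.3 defines NT-proBNP as percentage change at 72 h from admission, and aldosterone and renin activity as peak values. Section 3.5.4 defines VAS as change at 24, 48 and 72 h. Section 3.5.1 gives 24 h sodium in mmol.

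**The concern.** The design in section 3.1 gives 4 x 20 = 80 patients, so each randomised factor is compared 40 v 40. Precision is scarce at that size, and a baseline value that predicts the outcome recovers some of it without further patients or samples. A change score does this only in part. A raw peak does not do it at all, and hypothesis 2 (neurohumoral activation) rests on the peak hormones.

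For 24 h sodium the stake is what gets reported. Placing the Shapiro-Wilk sentence directly before the choice of test implies, though the text does not say so outright, that the trial data decide between a mean and a rank comparison. The measure of effect for the primary result would then be unknown until the data are seen.

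**Working it through.** **Inputs.** From the documents: 40 v 40 per factor (section 3.1) and two-sided 5% (section 3.6). The plan gives no power calculation, so it has no power figure to reproduce. All effects, SDs and correlations below are assumptions. The planned rule is read as Mann-Whitney if Shapiro-Wilk p < 0.05 in either group, otherwise the t-test. Simulations used 5,000 runs per cell unless stated.

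**VAS (analytic).** With equal SDs and baseline correlation r, the variance is 2(1-r) for a change score and 1-r² for ANCOVA, in units of SD². The ratio is (1+r)/2, so ANCOVA has 35/25/15% less variance at r = 0.3/0.5/0.7. Take a true difference of 0.5 SD and noncentrality d x sqrt(40/2), with 78 df for the change score and 80 - 4 = 76 df for ANCOVA (intercept, two factors, baseline):

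| r | d, change score | Power | d, ANCOVA | Power | Gain (points) |
|---|---|---|---|---|---|
| 0.3 | 0.5/sqrt(1.4) = 0.423 | 46% | 0.5/sqrt(0.91) = 0.524 | 64% | 18 |
| 0.5 | 0.5/sqrt(1.0) = 0.500 | 60% | 0.5/sqrt(0.75) = 0.577 | 72% | 12 |
| 0.7 | 0.5/sqrt(0.6) = 0.645 | 81% | 0.5/sqrt(0.51) = 0.700 | 87% | 6 |

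**NT-proBNP (simulated).** Log-SD 0.8, effect -0.35 on the log scale (exp(-0.35) = 0.70, about 30% lower):

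| r | Planned rule on % change | Log change, no baseline term | Log ANCOVA |
|---|---|---|---|
| 0.5 | 47% | 49% | 60% |
| 0.6 | 57% | 59% | 68% |
| 0.7 | 67% | 70% | 77% |
| 0.8 | 84% | 87% | 89% |

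Most of the gain comes from the baseline term and not from the log scale. A separate run gave 60 v 45% at r = 0.5 and 89 v 85% at r = 0.8, so the range is about 5-15 points within simulation error. With a smaller effect (25% lower), the planned rule gave 34/41/51/68% and log ANCOVA 45/51/61/75%. ANCOVA size was 0.049 (20,000 runs).

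**Peak aldosterone and renin activity (simulated).** Effect 0.5 log-SD. The planned rule gives 57-58% whatever the correlation. Log ANCOVA gives 59/63/71/87% at r = 0/0.3/0.5/0.7. A separate run gave 58/63/72/86% against 56-58%. The gain is about 1-30 points, and close to nothing if baseline does not predict the peak.

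**24 h sodium: how often the data switch the test.** With 40 per group, the rule picks Mann-Whitney in 9% of trials if sodium is exactly normal, and in 43/72/98% if it is log-normal with log-SD 0.2/0.3/0.5. With identical distributions in both groups the rule keeps its size (0.052-0.053, 20,000 runs).

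**24 h sodium: the choice of scale.** Multiplicative effect of 0.5 log-SD, no useful covariate, 4,000 runs:

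| Log-SD | Planned rule | mmol model |
|---|---|---|
| 0.4 | 57% | 55% |
| 0.5 | 58% | 54% |
| 0.6 | 58% | 52% |
| 0.8 | 57% | 46% |

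A log-scale model holds 58-59% throughout. For an additive shift of 0.5 SD with log-normal error (log-SD 0.8), the mmol model has 65% against 95% for the planned rule. Fixing the mmol scale therefore has a price once skew is moderate.

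**The case against.** The strongest reply is that baseline is already used where it matters: NT-proBNP is a percentage change and VAS a change score. That is correct. A reader might infer that the plan ignores baseline altogether, but this is true only of the peak hormones. The gain for the other two shrinks as correlation rises. These are also secondary or other outcomes, not primaries.

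A second tempting reading is that the normality pre-test inflates the type I error for sodium. The calculations do not show this when the two distributions are identical. One can build a case with equal means and a wider control spread (log-SD 0.5, 0.6 or 0.8 v 0.4) in which the rule rejects in 8/13/38% of trials. Its premise is that control patients receive "an intravenous bolus of loop diuretics at a dose equal to the double of his normal daily oral dose", while in the other group "the patient receives 500 mg of intravenous acetazolamide and 2 mg of intravenous bumetanide in bolus". Scaling the dose to the home dose could equally narrow the response, and the documents give no SD. With equal means and unequal log-SDs the distributions do differ, so a rank test that rejects is not giving a false positive. What stands is the unnamed effect measure.

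Third, the mmol unit in section 3.5.1 does not dictate a mean difference in mmol as the effect measure, and that scale can lose power. This stands, so the choice belongs to the sponsor. Adjusting sodium for home loop dose or eGFR is likewise not a clear gain: in simulation, power moved from 59 to 68% with a common dose slope (within-arm R² 20%), but from 60 to 59% with opposite slopes in the two groups.

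Finally, a reader might infer that section 3.5.2 pools hypo- and hyperkalaemia into one rate. Each has its own definition there, and the text can be read as two incidences, so pooling is not established.

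**Conclusion.** The point holds as a recommended improvement. Section 3.6 leaves collected baseline information partly or wholly unused and names no effect measure with a confidence interval. Baseline ANCOVA adds about 5-15 points of power for NT-proBNP, 1-30 for the peak hormones and 6-18 for VAS. These sizes rest on assumed effects (-0.35 log, 0.5 log-SD, 0.5 SD), an assumed log-SD of 0.8 for NT-proBNP, correlations of 0-0.8, and all 80 patients contributing. Sections 3.3.1 and 3.3.2 censor therapy-refractory patients, and how they enter any analysis is a separate matter that this change does not settle.

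For 24 h sodium the conclusion depends on no assumed number: one measure with its interval should be fixed in advance. The documents do not support going further, to a claim of lost error control or of invalid margin comparisons.

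**What to change.** Amend section 3.6 as follows.

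1. **72 h NT-proBNP, peak aldosterone, peak renin activity:** log scale, ANCOVA with the log baseline value and both randomised factors. Report ratios of geometric means with 95% CI. For NT-proBNP this keeps the relative-change meaning.
2. **VAS at 24, 48 and 72 h:** ANCOVA on baseline VAS with both factors. Report the difference with 95% CI.
3. **24 h sodium:** delete the Shapiro-Wilk choice of test. Before unblinding, name one effect measure with 95% CI, either the difference in mmol or the geometric-mean ratio. The sponsor chooses, knowing that the mmol scale loses power under moderate to strong skew. The other analysis is sensitivity only and cannot replace the primary. Adjustment for home loop dose or eGFR is optional: its gain is unknown and the dose slope may differ between groups.
4. **Potassium, at most:** report hypokalaemia and hyperkalaemia separately, to match hypothesis 3. Fisher's test can stay.

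The cost is SAP wording and about two degrees of freedom per model (78 to 76). It needs no new patients or measurements, because every baseline required is already in section 3.4.

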MRA have an established role in the treatment of chronic CHF.^{11, 12} However there are remarkable few data on their use in patients who present with ADHF. Nevertheless, in this context with frequent use of potassium wasting diuretics, they might be of particular interest to prevent occurrence of hypokalemia, which has been associated with a worse prognosis.²⁷ Moreover, by inhibiting distal tubular sodium reabsorption and counteracting aldosterone breakthrough, MRA might improve the natriuretic efficiency of loop diuretics.

2. Study Hypotheses

1. Combination therapy with acetazolamide improves loop diuretic efficacy to induce natriuresis in ADHF patients, allowing for a lower dose of the latter medication and potentially less adverse events such as worsening renal function.
2. Combination therapy with acetazolamide and low-dose loop diuretics leads to less pronounced neurohumoral activation compared to treatment with high-dose loop diuretics in ADHF patients.
3. Upfront therapy with MRA is safe in patients presenting with ADHF and lowers the incidence of hypokalemia and the need for potassium supplementation, without causing a higher incidence of hyperkalemia.
4. Combination diuretic therapy with acetazolamide and/or upfront spironolactone will lead to improved clinical outcome (less heart failure rehospitalizations and lower all-cause mortality).

3. Study Protocol

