3.5. Study end-points

3.5.1. Primary study end-point acetazolamide arm

Total urinary sodium excretion (mmol) after 24 h

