3.5.2. Primary study end-point for spironolactone arm

Incidence of hypo- (serum potassium <3.5mmol/L or need for oral/intravenous potassium supplements) or hyperkalemia (serum potassium >5.0mmol/L) during the entire 72 h interval after randomization.

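### The planned acetazolamide comparison has end-points for the adverse event expected to fall (renal) but none for metabolic acidosis, the one agent-specific harm the plan expects

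*Combined protocol and SAP*

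**What the plan says.** Section 2, hypothesis 1, is mainly about natriuresis, but it adds a comparative safety expectation for the combination: "allowing for a lower dose of the latter medication and potentially less adverse events such as worsening renal function".

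Section 4 names the harm on the other side: "Metabolic acidosis is the only agent-specific adverse event that might be expected from treatment with acetazolamide". It continues: "Serum bicarbonate is monitored daily" and "If serum bicarbonate <22 meq/L, substitution with oral NaHCO_3 will be provided".

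The primary end-point for the acetazolamide arm (3.5.1) is "Total urinary sodium excretion (mmol) after 24 h". The primary end-point for the spironolactone arm (3.5.2) is a potassium outcome: "Incidence of hypo- (serum potassium <3.5mmol/L or need for oral/intravenous potassium supplements) or hyperkalemia", over 72 h. Section 3.5.3 lists two renal outcomes, one up to 72 h and one at the visit 2-6 weeks after discharge. Section 3.5.4 includes therapy-refractory congestion, and all-cause mortality and readmissions at one year.

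Section 3.4 lists electrolytes at randomization and on days 1-3. It does not name bicarbonate or NaHCO3 administration. Section 3.6 gives general tests for continuous and categorical variables and describes no adverse-event analysis.

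**The concern.** A claim of fewer adverse events is a net claim: it needs the events expected to fall and those expected to rise. The plan identifies one of each for acetazolamide. It defines end-points, with thresholds and time windows, for the first and none for the second. A report that follows sections 3.5 and 3.6 could therefore show a renal benefit for the combination with no defined comparison of acidosis beside it.

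The plan handles its other factor differently. Hyperkalemia, the harm expected from spironolactone, is also monitored daily and managed under section 4, and it is still part of that arm's primary end-point. Monitoring is thus not treated as a substitute for an outcome there, and no reason is given for the difference.

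At stake is how far the trial can support the adverse-event part of hypothesis 1. The natriuresis result does not depend on it.

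**Working it through.** **1. Listed outcomes set against the harms.** The plan states no figure to reproduce, so the check is a count over sections 3.5.1 to 3.5.4.

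| Type of outcome | Number listed | Where |
|---|---|---|
| Renal function | 2 | 3.5.3 (before 72 h; 2-6 weeks after discharge) |
| Potassium | 1 | 3.5.2, designated for the spironolactone arm |
| Acidosis, bicarbonate or NaHCO3 use | 0 | none |
| Overall adverse events | 0 | none |

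Therapy-refractory congestion and one-year mortality and readmissions (3.5.4) could also reveal harm. They do not measure acidosis, and mortality and heart-failure readmission are the subject of hypothesis 4.

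**2. Size of the comparison.** Section 3.1 gives four groups of 20 in a 2x2 factorial. Each level of the acetazolamide factor has 2 x 20 = 40 patients, so the comparison is 40 v 40.

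**3. What an unlisted excess could look like.** The documents give no acidosis rates; all counts here are assumptions. The interval is Newcombe's, built from the Wilson limits (l, u) of each proportion p, with group 1 receiving acetazolamide:

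- lower = (p1 - p2) - sqrt[(p1 - l1)² + (u2 - p2)²]
- upper = (p1 - p2) + sqrt[(u1 - p1)² + (p2 - l2)²]

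*10/40 v 2/40.* p1 = 0.25 (Wilson 0.142 to 0.402); p2 = 0.05 (0.014 to 0.165).
- lower = 0.20 - sqrt(0.108² + 0.115²) = 0.042
- upper = 0.20 + sqrt(0.152² + 0.036²) = 0.356
- Excess of 20 points, 95% CI 4.2 to 35.6; Fisher p = 0.025.

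*16/40 v 4/40.* p1 = 0.40 (0.263 to 0.554); p2 = 0.10 (0.040 to 0.231).
- Excess of 30 points, 95% CI 11.1 to 46.5; Fisher p = 0.004.

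**4. Whether 40 v 40 would be informative.** Exact power of the two-sided Fisher test at 0.05 (the test and level in section 3.6), for assumed rates:

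| Control rate | Acetazolamide rate | Power |
|---|---|---|
| 5% | 20% / 30% / 40% | 41% / 82% / 97% |
| 10% | 30% / 40% / 50% | 53% / 85% / 98% |
| 20% | 40% / 50% / 60% | 41% / 75% / 95% |

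A large excess would probably be detected and a moderate one often would not, so the interval matters more than the p-value. With 0 events in 40, the one-sided 95% upper limit for the rate is 1 - 0.05^(1/40) = 7.2%.

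**5. Form of the outcome.** Because NaHCO3 is provided below 22 meq/L, bicarbonate values after that point are partly corrected. An outcome based on later values alone would understate the effect, so NaHCO3 use has to count as an event. A patient already below 22 meq/L at randomization should not count on the bicarbonate criterion, so that criterion must be for new values.

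**The case against.** The strongest reply is that hypothesis 1 is hedged, its main claim is natriuresis, and the one adverse event it names as an example has its own end-points. The plan does not commit its authors to a general statement about adverse events. Bicarbonate is measured daily, so the data should exist, and nothing forbids reporting acidosis. All of this is fair, and it is why the point concerns a subsidiary claim. It does not close the gap: nothing in the plan requires an acidosis comparison or fixes its threshold, window or groups.

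Several stronger readings are tempting, and the documents do not support them.

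- *That the safety assessment is one-sided, resting on a single renal outcome.* There are two renal outcomes; therapy-refractory congestion, mortality and readmissions can also show harm; and tests are two-sided.
- *That an acidosis excess could outweigh any fall in worsening renal function.* The documents give no rate for either event. A bicarbonate threshold and a creatinine-defined event are also not interchangeable point for point.
- *That the Background identifies the Arm 1 drugs as the cause of potassium loss.* It speaks of potassium-wasting diuretics in general and does not say which. Arm 1 does change the loop-diuretic regimen, so splitting the potassium counts by that factor is sensible. The plan's silence on it is a minor omission.
- *That NaHCO3 use goes unrecorded.* The case report form and Addendum 1 are not in the supplied text, so this cannot be known.

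**Conclusion.** The point holds as a pre-specification gap that should be closed. The plan names one agent-specific harm expected from acetazolamide, monitors and treats it, and includes it in no primary, secondary or other pre-specified outcome. The adverse event expected to fall has two end-points. The adverse-event part of hypothesis 1 is therefore only partly tested by the listed outcomes.

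Neither primary end-point is affected. The size of any missed excess is unknown: the 20- and 30-point examples rest on assumed counts and on the planned 40 v 40 being achieved. They show that an excess large enough to be detected at this sample size could be absent from every listed outcome, and nothing about how likely that is.

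**What to change.** Three additions; no dose, threshold or treatment rule changes.

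1. In 3.5.3 or 3.5.4, add a safety outcome for Arm 1: new serum bicarbonate below 22 meq/L (not present at randomization) or any NaHCO3 given, within 72 h. Compare it by acetazolamide group with a risk difference and 95% CI. Any comparison of lowest bicarbonate should be supportive only, because NaHCO3 modifies later values.
2. In 3.4, name bicarbonate explicitly, including in the randomization sample, and name NaHCO3 use. Section 4 promises daily monitoring but does not say that a randomization value is taken, and the new-onset condition needs one.
3. Tabulate the hypo- and hyperkalemia counts of 3.5.2 by Arm 1 group as well.

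The cost is a few table rows and data fields for bicarbonate and NaHCO3 if the case report form lacks them. If the electrolyte panel at randomization does not already include bicarbonate, one more assay on that sample is needed. The safety statement for the combination may also be less favourable if acidosis proves common.

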3.5.4. Other pre-specified outcome measures

- Total urinary sodium excretion (mmol) after 48 h and 72 h
- Total urine output after 24 h, 48 h and 72 h
- Change in VAS score for dyspnea at 24 h, 48 h and 72 h
- Change in 4-point Likert scale for edema at 24 h, 48 h and 72 h
- Body weight change upon hospital discharge compared to admission
- Incidence of therapy-refractory congestion defined as the need for combinational diuretic therapy with chlorthalidone, bail-out ultrafiltration or renal replacement therapy

- Incidence of all-cause mortality and readmissions after 1 year

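### Does the unlisted use of oral NaHCO₃ undermine the urinary sodium comparison for acetazolamide?

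*Combined protocol and SAP*

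**What the plan says.** Under potential adverse events (Section 4), the plan says: "Metabolic acidosis is the only agent-specific adverse event that might be expected from treatment with acetazolamide". Serum bicarbonate is checked daily, and the rule for acting on it reads: "If serum bicarbonate <22 meq/L, substitution with oral" NaHCO₃. The rule is not confined to one group, and no dose, frequency or duration is given.

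The primary end-point for the acetazolamide comparison (Section 3.5.1) is "Total urinary sodium excretion (mmol) after 24 h". Section 3.5.4 adds "Total urinary sodium excretion (mmol) after 48 h and 72 h" among the other pre-specified outcomes. All three are gross amounts, not net of intake.

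Section 3.4 lists medical therapy only in the baseline set ("Demographics, medical history, current medical therapy, baseline body weight"). For days 1–3 the nearest item on intake is "Body weight and fluid balance". On urine it says: "Three consecutive 24h urinary collections will be performed; the first one started with the first bolus administration of loop diuretics". Section 3.6 compares groups with an unadjusted t-test or Mann-Whitney U test.

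**The concern.** The protocol supplies a sodium salt in response to an effect expected of one study drug, and then measures sodium in the urine. If more acetazolamide patients are supplemented, part of any excess urinary sodium in that group may have come from the supplement rather than from the diuretics. The expected direction favours acetazolamide.

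Hypothesis 1 in Section 2 is about natriuresis produced by the diuretic combination, and Section 1 gives negative sodium balance as the treatment target. Supplement sodium that passes into the urine raises the gross figure without making the balance more negative. With no dose or time in the Section 3.4 list, a reader could fear that the size of this contribution can never be known. The 48 h and 72 h totals, which would show whether natriuresis is sustained, look the most exposed.

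**Working it through.** **1. Timing.** Section 3.3.2 starts the drug at time zero ("At the moment of randomization, the patient receives 500 mg of intravenous acetazolamide"), and the first urine collection starts with the first loop diuretic bolus. Acidosis caused by the drug would normally be seen at a daily check after that bolus, so most supplement sodium should fall after the first 24 h. This is an inference. A patient already below the threshold at baseline could be supplemented on day 1.

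**2. Is Section 3.4 a complete record of treatments?** Set beside the end-points, it is not:

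- Potassium supplements on days 1–3 are part of the spironolactone primary end-point (Section 3.5.2), but Section 3.4 does not list them.
- Chlorthalidone, ultrafiltration and renal replacement define an outcome in Section 3.5.4, and Sections 3.3.1 and 3.3.2 link them to censoring. They are not listed either.
- Doses of study drug actually given are not listed.

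The plan's own end-points need the first two groups of items, so they must be recorded elsewhere. The case report form (Section 3.1) and Addendum 1 (Section 3.3) are not in the supplied text.

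**3. What the listed data already show.** If the rule is followed, daily bicarbonate identifies who met the trigger and from which day. Patients who never met it contribute zero. Only the amount given to those who did remains unknown.

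**4. Size.** The plan has no figure to reproduce. The inputs below are assumptions, except the molar mass (84.0 g/mol) and the group size (four groups of 20, so 40 against 40 on the acetazolamide margin).

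- Sodium per gram of NaHCO₃: 1000 / 84.0 = 11.9 mmol.
- Middle case: 3 g/day, 25 percentage points more use with acetazolamide, half excreted. Shift per day of supplementation = 11.9 × 3 × 0.25 × 0.5 = 4.46 mmol.
- Days of supplementation by 24, 48 and 72 h: 0.5, 1.5 and 2.5.
- Yardstick: the detectable difference is 0.634 × SD (two-sided 0.05, 80% power). Daily SD is 100–130 mmol with between-day correlation 0.5, so the cumulative SD is multiplied by √3 at 48 h and √6 at 72 h.

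| | 24 h | 48 h | 72 h |
|---|---|---|---|
| Shift, middle case (mmol) | 2.2 | 6.7 | 11.2 |
| SD (mmol) | 100–130 | 173–225 | 245–318 |
| Detectable difference (mmol) | 63–82 | 110–143 | 155–202 |
| Shift as share of detectable | 3–4% | 5–6% | 6–7% |
| Shift at 25% excreted (mmol) | 1.1 | 3.3 | 5.6 |
| Shift at 100% excreted (mmol) | 4.5 | 13.4 | 22.3 |

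A full first day of supplementation in the middle case gives 4.46 mmol at 24 h, or 5–7% of the detectable difference (4.46/82 to 4.46/63).

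Stacked extreme: 6 g/day, 50 points more use, all excreted. This gives 11.9 × 6 × 0.50 × 1 = 35.7 mmol per day, hence 17.9, 53.6 and 89.3 mmol. At 72 h that is 44–58% of the detectable difference (89.3/202 to 89.3/155). None of these cases is a ceiling. The documents cap neither supplement dose nor start time, and Section 3.3.2 lets the larger acetazolamide dose continue when diuresis is low.

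**5. Would subtracting supplement sodium help?** Let d be the between-group difference in mean supplement sodium given and f the fraction excreted. As a measure of diuretic-induced sodium, the gross result is off by +f·d and the subtracted result by −(1−f)·d. The two are equal in size at f = 0.5. In the middle case at 72 h, d = 11.9 × 3 × 0.25 × 2.5 = 22.3 mmol. At f = 0.25 the gross error is +5.6 and the subtracted error −16.7 mmol, so subtraction is the worse of the two.

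**The case for a change.** The strongest case for acting is that it costs little. One field for dose and time, and one table by group, would settle a question that bicarbonate values alone cannot, because the amount given is not fixed by the protocol. Urinary chloride does not rescue the position, since acetazolamide itself raises urinary bicarbonate. In a trial of 80 patients whose primary end-point is sodium, accounting for sodium given by protocol seems proportionate, and the listed data do not strictly exclude the extreme case.

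Part of this stands. The amount given is indeed missing from Section 3.4, and a table by group would help in reading the 48 h and 72 h results. But that is reporting detail that the analysts can supply, and the case report form may already hold it.

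The argument does not show that the planned comparison is wrong. For the end-point as defined, a difference that arises through protocol-provided NaHCO₃ is an effect of the regimen, and the type I error is not inflated. Error rates above 5% can be computed only for a different quantity, natriuresis due to the diuretics alone, which is not a planned end-point. Even then the middle case gives about 5.1% at 24 h and at most 5.5% at 72 h.

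Nor does the argument justify a pre-specified subtraction. That would adjust for something treatment affects after randomisation, would give neither a net balance (dietary sodium is unmeasured) nor a causal diuretic effect, and can move further from the truth than the gross figure.

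**Conclusion.** No change to the plan is needed. Followed as written, it gives a sound primary result: a randomised comparison of gross 24 h sodium excretion under two regimens. The likely supplement contribution is about 2 mmol at 24 h, against a detectable difference of 63–82 mmol. It is somewhat larger at 48 h and 72 h, in outcomes that are neither primary nor secondary.

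These sizes rest on assumed supplement dose, excess use, excreted fraction, duration and SD. Higher use with acetazolamide is expected rather than certain. If use were very heavy and nearly all the sodium were excreted, the later totals would need cautious reading.

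It would be good practice, though optional, to confirm that NaHCO₃ dose and time are recorded and to report the number supplemented and the mmol given by acetazolamide group for each 24 h period. Any subtraction is best shown only as an exploratory bound beside the gross result.
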